# **Study Protocol, Statistical Analysis Plan, and Informed Consent for**

## **Utilization of Hepatitis C Positive Kidneys in Negative Recipients**

### **(USE-Hep C)**

#### **I. Objectives**

To evaluate the safety and feasibility of transplanting kidneys from Hepatitis C virus (HCV) infected donors into recipients without HCV infection

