### **III. Procedures**

**a. Research design:**

This will be an open label, prospective, interventional, proof of concept study to evaluate the feasibility and safety of kidney transplant from HCV positive donors into HCV negative donor using Sofosbuvir/Velpatasvir as the preferred treatment choice for post-transplant HCV transmission.

The Ohio (OSUMC) has performed HCV+ into HCV- recipient liver transplants as standard of care since February of 2019. OSUMC has also been performing transplant of liver and kidneys from donors who are HCV antibody positive but PCR negative (non-viremic donors) since 2016. In order to present an overall picture of the patient outcomes across multiple types of organ transplants using HCV+ organs, we would like to review data from these liver and kidney transplant patients. To do so, retrospective data from recipients of HCV positive into negative liver transplants, and HCV antibody positive but PCR negative liver and kidney transplant recipients will be analyzed. Patients who were treated between January 19th, 2016 and November 26th, 2019 will be included in our analysis.

In order to confirm the safety of transplants using HCV+ kidneys, we will compare the outcomes of transplant from HCV viremic donors (HCV PCR+) to those from HCV non viremic donors (donors with HCV antibody neg/PCR negative and HCV antibody positive/PCR negative). To do so, we will retrospectively review charts of patients who received a kidney transplant at OSU between 1/1/2018 and 8/1/2020. This review will include recipients of HCV antibody negative/PCR negative (antibody (ab)-/Nucleic Antigen Test (NAT)-), HCV antibody positive/PCR negative (ab+/Nat-), and HCV antibody positive/PCR positive (ab+/Nat+).

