**b. Study sample:**

The study will aim to enroll 55 patients. Given the fact this is a proof of concept study, a sample size cannot be calculated based on power analysis.

Patients will be screened by a research nurse after completion of their pre-transplant evaluation. Patient who meets all inclusion and none of the exclusion criteria will be approached for consent. The consent will be discussed and explained to patient by a physician or research coordinator.

Inclusion criteria:

Adult age >18 years able to provide consent

Lack of available living donor

Calculated pre-transplant reactive panel (cPRA) of <80%

Estimated post-transplant survival (EPTS) index >20% and <80%

Negative pre-transplant HIV, HCV, and HBV serology and blood PCR

No clinically significant pre-transplant liver disease

Contraception based on the REMS protocol

Agree to abstinence from alcohol for at least 6 months post-transplant

Exclusion criteria:

Living donor available

Dialysis time >5 years

History of previous organ transplantation  
Listing for multi-organ transplantation  
Active or recent history (<6 months) of alcohol or substance abuse  
Clinically significant liver disease as determined by principal investigator  
History of hepatocarcinoma  
Pregnancy or lactation  
Refusal to accept blood transfusion  
HIV infection  
HCV pcr or antibody positive  
HBV infection  
Any condition that in the opinion of the investigator would impair the patients' ability to comply with the study procedures  
Donor selection criteria:  
Positive HCV PCR at time of donation  
KDPI<85%

For the retrospective chart review of HCV+ liver/HCV- recipients and HCV antibody positive/PCR negative liver and kidney transplant recipients, we aim to review 78 charts. The Ohio State University has so far performed 11 HCV+ into negative liver transplant, 25 HCV ab+/PCR negative kidney transplant and 25 HCV ab+/PCR negative liver transplant so far., Since this is a retrospective chart review portion of the study, a waiver of consent and HIPAA authorization will be requested for this portion of the study.

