**c. Measurements/End points:**

Primary efficacy end point is the proportion of patients with undetectable HCV PCR at 12 weeks after completion of HCV treatment with Sofosbuvir/Velpatasvir

Primary safety end point: The incidence of adverse events related to DAA treatment

Secondary end points:

eGFR and serum creatinine at 6 and 12 months post-transplant

Patient's survival at 6 and 12 months

Graft's survival at 12 months

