  - a. Sofosbuvir/Velpatasvir will be first line therapy. Treatment will be with one tablet a day for 12 weeks.
  - b. Glecacrevir/Pibrentasvir will be a second line therapy for patients with delayed graft function or poor graft function (eGFR <30) two weeks post-transplant. Glecacrevir/Pibrentasvir doesn't require renal dose adjustment. Treatment will be with 3 tablets daily for 12 weeks.
  - c. Other FDA approved DAAs could be utilized as potential third line therapies if the first and second line therapies are not approved by insurance or patient could have a potential drug to drug interactions
  - d. Patient will receive follow up HCV PCR on week 4 and week 12 of therapy. HCV PCR will be repeated on week 12 following completion of DAA therapy.

3. Clinic schedule follow up:

- I. Patient will be seen in the transplant clinic per routine post-transplant protocol; weekly x4, then on weeks 6, 9 and 12, then months 4,6,9 and 12, 18 and 24.

- II. Patient will be seen by Hepatology only if the patient is symptomatic for HCV.
- 4. Laboratory schedule:
  - I. Patient will have CBC, Chem-7, and Tacrolimus trough levels drawn twice weekly for the first 12 weeks, then once a week 3-6 months, then every two weeks 6-12 months, then once a month thereafter (standard of care)
  - II. Liver function test (LFTs), Prothrombin time (PT), and Partial Thromplastin Time (PTT) will be checked weekly for the first 12 weeks then quarterly per center protocol
  - III. HCV PCR will be checked on week 4 and week 12 of therapy. HCV PCR will be repeated on week 12 following completion of DAA therapy then quarterly for one year Lipid profile, HbA1c, iron studies and alloscreen will be checked per center protocol
- e. **Data and statistical analysis:**
  - I. Data presented will be mostly a descriptive data giving low number of enrolled patient and lack of adequate power analysis
  - II. We will collect the following data points for retrospective chart review:
    - a. **Recipient:** medical record number, transplant date, patient demographics, blood type, End-stage liver disease etiology, Model for end stage liver disease (MELD) score at transplant, end stage renal disease etiology, time of dialysis prior to transplant, CMV status for donor and recipient, Epstein-Barr virus (EBV) status, and post-transplant HCV activation, and post-transplant treatment information
    - b. **Donor:** demographics, cause of death, CMV status, EBV status, HCV genotype

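### The two primary endpoints cover different, nested sets of patients (cure after completing sofosbuvir/velpatasvir, harm on any DAA), so the two figures cannot be paired

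*Combined protocol and SAP*

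**What the plan says.** Section III.c names two primary endpoints. Efficacy is the proportion of patients with "undetectable HCV PCR at 12 weeks after completion of HCV treatment with Sofosbuvir/Velpatasvir". Safety reads "Primary safety end point: The incidence of adverse events related to DAA treatment". The first names one drug and requires completion. The second names no drug and gives no denominator.

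Section III.d.2, item III, provides three lines of treatment:

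- Item a: "Sofosbuvir/Velpatasvir will be first line therapy".
- Item b: glecaprevir/pibrentasvir "will be a second line therapy for patients with delayed graft function or poor graft function (eGFR <30) two weeks post-transplant".
- Item c: other approved DAAs "if the first and second line therapies are not approved by insurance or patient could have a potential drug to drug interactions".

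Section II.b describes the same graft-function and insurance routes. It also lists sofosbuvir/velpatasvir among the third-line options, although it is the first choice in both sections.

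The objective in Section I is "To evaluate the safety and feasibility of transplanting kidneys from Hepatitis C virus (HCV) infected donors into recipients without HCV infection". Section III.a repeats it, "using Sofosbuvir/Velpatasvir as the preferred treatment choice for post-transplant HCV transmission". Section III.e promises mostly descriptive data. It defines no efficacy or safety population and no table by drug, and it does not say how a recipient on another DAA counts for efficacy.

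**The concern.** A single-arm, descriptive study of this kind will be read by putting its cure rate next to its adverse-event rate. That works only if both rates describe the same patients. Here the cure rate describes those who completed one drug. The harm rate describes everyone treated with any DAA, including those who stopped early. The additional patients are not a random sample: they received another regimen because of poor graft function, an insurer's decision or co-medication.

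Two things are at stake. First, a reader may take the all-DAA rate as the harm rate of the preferred drug and credit it with more patients than support it. Second, recipients moved to another regimen count for harm but have no place in primary efficacy, so the study has no primary cure figure for the strategy as a whole.

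**Working it through.** The plan has no figure to reproduce. The planned 55 has no power or precision calculation behind it. The check therefore sets the texts side by side and then illustrates the size.

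**Who is in each set**

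| Recipient | Primary efficacy | Primary safety |
|---|---|---|
| Completes sofosbuvir/velpatasvir | in | in |
| Starts it, stops early | out, as worded | in |
| Glecaprevir/pibrentasvir (graft function) | out | in |
| Other DAA (insurance, interaction) | out | in |

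The safety denominator is not stated, so its column is the natural reading of an endpoint defined on DAA treatment. On that reading the sets are nested.

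**Inputs**

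- From Section III.b: "The study will aim to enroll 55 patients". This is a ceiling on the number treated. Consent precedes transplant, and Section III.d.2 provides for recipients who are still PCR-negative at discharge.
- Assumed, because the documents give neither: a share s of 20% to 40% on another DAA, and related events in 10% of sofosbuvir/velpatasvir recipients and in a proportion r of the others.

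The sofosbuvir/velpatasvir set is then 55 × 0.8 = 44 down to 55 × 0.6 = 33.

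**How far the pooled rate can sit from the drug's own rate**

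Pooled rate = (1 − s) × 0.10 + s × r.

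| r on other DAAs | s = 0.2 | s = 0.4 |
|---|---|---|
| 0% | 0.08 + 0 = 8% | 0.06 + 0 = 6% |
| 10% | 0.08 + 0.02 = 10% | 0.06 + 0.04 = 10% |
| 20% | 0.08 + 0.04 = 12% | 0.06 + 0.08 = 14% |
| 30% | 0.08 + 0.06 = 14% | 0.06 + 0.12 = 18% |

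So a true 10% could appear as anything from 6% to 18% under these assumptions, and as exactly 10% if the rates are equal.

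**How many patients support the figure**

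This part needs no assumed event rate for either group, only a share on other DAAs. With zero events among n, the exact (Clopper-Pearson) two-sided 95% upper limit is 1 − 0.025^(1/n). By the same formula, if all n are cured the lower limit is 0.025^(1/n).

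| n | Upper limit, no events | Lower limit, all cured |
|---|---|---|
| 55 | 6.5% | 93.5% |
| 44 | 8.0% | 92.0% |
| 33 | 10.6% | 89.4% |

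**The case against.** The strongest reply is that the safety endpoint is the right one. The objective concerns a transplant strategy, and sofosbuvir/velpatasvir is only its preferred drug. Recipients who need another DAA are part of that strategy, so harm should be counted over all of them. This stands. A reader might infer that safety should be narrowed to sofosbuvir/velpatasvir, but the documents do not support that. Recipients with delayed graft function who are given another DAA would then fall outside both headline figures. A one-dose safety denominator would also still not match an efficacy endpoint measured after completion.

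A reader might also infer that the pooled rate is biased upward because recipients with poorer grafts receive the other drugs. The documents do not support this either. The endpoint counts only DAA-related events, recipients switched by an insurer need not be sicker, and Section II describes both main drugs as very well tolerated.

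Nor does the plan state a decision to pool. Pooling follows from the absence of any breakdown by drug, and such tables are not ruled out.

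Finally, the study is descriptive and tests no hypothesis on either endpoint. That limits the severity. It does not remove the point, because in a descriptive study the choice of denominators and groupings is the analysis. Stating a denominator for the all-DAA rate alone would leave the two endpoints unmatched.

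**Conclusion.** The point holds as a mismatch of scope. As worded, the two primary figures describe nested but different patient sets and cannot be paired. This follows from the endpoint wording and the treatment lines. It requires only that some recipients stop early or receive another DAA.

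It would go too far to say that the two endpoints are measured on different people, since completers of sofosbuvir/velpatasvir are in both sets. It would also go too far to say that the reported harm rate will be wrong. Its distance from the drug's own rate is unknown in size and direction, and the 6% to 18% range rests entirely on assumed shares and rates. The difference in precision, 6.5% against 8.0% to 10.6% with no events, rests on the assumed 20% to 40% share and on 55 as a ceiling.

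Sample size and error rates are unaffected. This is an inexpensive improvement to how two primary endpoints are defined and reported.

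**What to change.** In Section III.c, keep the all-DAA safety figure and report both primary outcomes on the same two sets:

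- (a) all recipients who took at least one dose of any DAA;
- (b) recipients who started sofosbuvir/velpatasvir.

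Show glecaprevir/pibrentasvir and other DAAs beside them. For each set, count patients with at least one DAA-related adverse event, and patients with undetectable HCV PCR 12 weeks after the end of treatment, whether or not the course was completed. Classify each patient by the first regimen started. Give exact 95% limits. State that differences between regimens are not comparative, because the regimen follows graft function, coverage and co-medication.

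Sections II.b and III.d.2 must be reconciled on where sofosbuvir/velpatasvir sits in the treatment lines before set (b) is defined.

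The cost is a few sentences in III.c and extra table columns, with no added patients and no change in treatment. The post-treatment PCR in III.d.2 is already scheduled for DAA recipients generally, but it is timed from completion, so the wording should also cover those who stop early. Section III.e lists treatment information only for the chart review, so the plan should say that regimen and start and stop dates are recorded for prospective patients too. The downside is smaller denominators and wider limits per regimen, as in the last table above.

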**d. Detailed study procedures:**

After completion of post-transplant evaluation and signing informed consent, patient status at UNOS will be changed to "Willing to accept HCV+ organ". Once an organ become available, it will be offered to the patients on HCV+ list per UNOS points system. Care following receiving HCV+ donor kidney for study patients will be as follow

1. Induction/maintenance therapy:

- I. Patient will receive induction with Thymoglobulin (rabbit ATG) for a total dose of 4-6 mg/kg per routine center protocol. Thymoglobulin induction will be started on day 0 after transplant surgery.
- II. Maintenance immunosuppressive therapy: patient enrolled in the study will receive the same routine maintenance immunosuppressive therapy used for recipients of HCV negative kidneys in our center. Maintenance

therapy will be started on post-operative day 1 with Tacrolimus, Mycophenolic acid, and rapid prednisone taper. Tacrolimus will be started at a weight based total dose of 0.15 mg/kg divided into two daily doses 12 hours apart. Trough levels will be checked daily prior to morning dose while inpatient and dose will be adjusted to target trough level of 8-12 for the first three months. Trough levels target in enrolled patients will follow our center post-transplant Tacrolimus trough target. Mycophenolic acid will be started at dose of 720 mg twice daily on post-Operative day one and continued long term. Dose can be adjusted/reduced per patient's primary transplant physician as appropriate due to side effect or infectious complications. Prednisone therapy will be tapered off by day 4 per center protocol

2. Hepatitis C evaluation and treatment:

- I. Recipients will have HCV PCR checked on admission day 0 prior to kidney transplant, and on day 3 prior to discharge. Patient with negative HCV PCR prior to discharge will have PCR checked weekly for 8 weeks then monthly up to 12 months post-transplant until PCR is positive. Checks will be stopped once PCR is positive. Patients with positive HCV PCR at day 3 post-transplant will not have further weekly or monthly checks but will follow the during treatment/post-treatment HCV PCR schedule mentioned below in section 2.3.d.
- II. Hepatology consult will be placed automatically on day 0 of transplant index admission and again if the patient is symptomatic for HCV.
- III. Direct acting anti-viral drugs (DAAs) will be initiated within eight weeks of first positive HCV PCR.
  - a. Sofosbuvir/Velpatasvir will be first line therapy. Treatment will be with one tablet a day for 12 weeks.
  - b. Glecacrevir/Pibrentasvir will be a second line therapy for patients with delayed graft function or poor graft function (eGFR <30) two weeks post-transplant. Glecacrevir/Pibrentasvir doesn't require renal dose adjustment. Treatment will be with 3 tablets daily for 12 weeks.
  - c. Other FDA approved DAAs could be utilized as potential third line therapies if the first and second line therapies are not approved by insurance or patient could have a potential drug to drug interactions
  - d. Patient will receive follow up HCV PCR on week 4 and week 12 of therapy. HCV PCR will be repeated on week 12 following completion of DAA therapy.

3. Clinic schedule follow up:

- I. Patient will be seen in the transplant clinic per routine post-transplant protocol; weekly x4, then on weeks 6, 9 and 12, then months 4,6,9 and 12, 18 and 24.

- II. Patient will be seen by Hepatology only if the patient is symptomatic for HCV.
- 4. Laboratory schedule:
  - I. Patient will have CBC, Chem-7, and Tacrolimus trough levels drawn twice weekly for the first 12 weeks, then once a week 3-6 months, then every two weeks 6-12 months, then once a month thereafter (standard of care)
  - II. Liver function test (LFTs), Prothrombin time (PT), and Partial Thromplastin Time (PTT) will be checked weekly for the first 12 weeks then quarterly per center protocol
  - III. HCV PCR will be checked on week 4 and week 12 of therapy. HCV PCR will be repeated on week 12 following completion of DAA therapy then quarterly for one year Lipid profile, HbA1c, iron studies and alloscreen will be checked per center protocol
- e. **Data and statistical analysis:**
  - I. Data presented will be mostly a descriptive data giving low number of enrolled patient and lack of adequate power analysis
  - II. We will collect the following data points for retrospective chart review:
    - a. **Recipient:** medical record number, transplant date, patient demographics, blood type, End-stage liver disease etiology, Model for end stage liver disease (MELD) score at transplant, end stage renal disease etiology, time of dialysis prior to transplant, CMV status for donor and recipient, Epstein-Barr virus (EBV) status, and post-transplant HCV activation, and post-transplant treatment information
    - b. **Donor:** demographics, cause of death, CMV status, EBV status, HCV genotype
  - III. [] This will also be a descriptive analysis. Continuous variables will be expressed as median and interquartile ranges. Discrete variables will be expressed as percentage. Any p-values will be significant if <0.05

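### Liver tests are not tied to the start of DAA therapy: on the likely (transplant) clock, weekly testing covers anywhere from 96% to 0% of the treatment period that the primary safety endpoint concerns

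*Combined protocol and SAP*

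**What the plan says.** Section III.c defines the outcome: "Primary safety end point: The incidence of adverse events related to DAA treatment". The period of interest therefore opens with the first DAA dose.

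The timing of therapy is in section III.d, item 2. PCR is checked on the day of transplant and again "on day 3 prior to discharge". A patient who is still negative "will have PCR checked weekly for 8 weeks then monthly up to 12 months post-transplant until PCR is positive". Item 2.III then says: "Direct acting anti-viral drugs (DAAs) will be initiated within eight weeks of first positive HCV PCR". The first-line and second-line regimens each run for 12 weeks.

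The laboratory schedule is item 4 of the same section:

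- Item 4.I, labelled standard of care: CBC, Chem-7 and tacrolimus levels are "drawn twice weekly for the first 12 weeks, then once a week 3-6 months, then every two weeks 6-12 months", and monthly after that.
- Item 4.II: liver function tests (LFTs), PT and PTT "will be checked weekly for the first 12 weeks then quarterly per center protocol".
- Item 4.III: "HCV PCR will be checked on week 4 and week 12 of therapy", again 12 weeks after completion, and then quarterly for one year.

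Clinic visits (item 3) follow the routine post-transplant calendar. Hepatology is consulted on day 0 and otherwise only for HCV symptoms. The documents give no separate schedule for collecting adverse events.

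**The concern.** A drug-safety incidence can be interpreted only if patients are observed in a comparable way while they take the drug. Here the drug starts on a date that varies between patients, and no liver test is fixed to that date. If the weekly block of liver tests is counted from transplant, it is used up by week 12 whether or not therapy has begun. A patient treated early would be tested nearly every week on therapy, and a patient treated late hardly at all.

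Two things are at stake. Asymptomatic enzyme rises on therapy may go unseen. A single pooled incidence would also combine patients with very different chances of having such an event detected, so a low rate could partly reflect absent testing. That matters in a proof-of-concept study whose stated objective includes safety.

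**Working it through.** The plan states no coverage figure, so there is nothing to reproduce. The check is a calendar overlap.

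**Which clock.** Item 4.II names no anchor. Item 4.I uses the same opening 12-week block and continues in months, as standard of care, which fits transplant. Item 4.III names therapy explicitly when therapy is meant. Transplant is therefore the natural reading, but it is an inference.

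**Inputs.**

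- First positive PCR: day 3 at the earliest, then at weekly checks for 8 weeks, then monthly to month 12 (item 2.I).
- Lag from first positive to DAA start: 0 to 56 days (item 2.III).
- Therapy: 12 weeks = 84 days (items 2.III.a and 2.III.b).
- Weekly LFT block: 84 days from transplant (item 4.II, on the transplant reading).
- Assumptions: weekly tests fall at weeks 1 to 12. Quarterly tests fall every 13 weeks, either counted from week 12 (weeks 25, 38, ...) or at months 6, 9, 12 (weeks 26, 39, 52). Both variants were run.

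**Formula.** Start day s = day of first positive + lag. Therapy days under weekly testing = max(0, 84 − s). Cover = that number / 84.

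| DAA start (day) | How it can arise | Days covered | Cover |
|---|---|---|---|
| 3 | positive day 3, no lag | 81 | 96% |
| 14 | illustrative: the two-week point at which graft function decides on second-line therapy | 70 | 83% |
| 17 | positive day 3, lag 14 | 67 | 80% |
| 31 | positive day 3, lag 28 | 53 | 63% |
| 45 | positive day 3, lag 42 | 39 | 46% |
| 59 | positive day 3, lag 56 | 25 | 30% |
| 84 | positive day 28, lag 56 | 0 | 0% |

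Cover is below one half when 84 − s < 42, that is, for any start after day 42 (week 6).

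**What remains after week 12.** With a day-59 start, therapy ends on day 59 + 84 = 143 (week 20.4). The next quarterly test is at week 25 or 26, so the last 143 − 84 = 59 therapy days (70%) have no scheduled liver test. With a start exactly at week 12, therapy runs to week 24. The week-12 test coincides with the start, and no liver test is scheduled after it during therapy under either quarterly variant. With a start at week 16, therapy runs to week 28 and contains one quarterly test. Since 84 days is shorter than 13 weeks (91 days), no start on or after day 84 can have more than one.

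**Late first positives.** If the first monthly check falls one month after week 8 (8 + 52/12 = 12.3 weeks), every patient first positive at a monthly check has 0% weekly cover whatever the lag.

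**Other contact.** Scheduled clinic visits during therapy number 7 for a day-3 start, 3 for a day-59 start, and 0 to 2 for starts at week 12 or later.

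**The other reading.** If the 12-week block were counted from DAA start, cover would be 84/84 = 100% for every patient.

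**The case against.** The strongest reply is that the gap rests on an inferred anchor and on permitted extremes. The anchor is indeed unstated, and under the other reading the gap vanishes. Eight weeks is a ceiling, not a planned delay. The plan expects near-certain transmission, and its choice of agent turns on graft function at one to two weeks after transplant, which suggests that early treatment is contemplated. A day-7 start gives 77/84 (92%) and a day-14 start 83%. All of this stands. It limits what can be said about how many patients are affected, but it does not tie any liver test to therapy, and the plan itself foresees causes of delay such as insurance denial.

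It is also fair that observation does not stop. Clinic visits run to month 24, CBC and Chem-7 continue throughout, and unscheduled LFTs are not barred. Symptomatic events can surface this way. Because the plan lists LFTs separately from CBC and Chem-7, those panels as written do not fill the gap.

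A reader might infer four stronger things that the documents do not support:

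- **That the primary safety endpoint as a whole goes unobserved.** The gap concerns asymptomatic liver events detected by laboratory test.
- **That the reported incidence will be too low.** It may be. Without start dates, neither the occurrence nor the size of the bias is shown, and the plan does not say whether laboratory changes count as adverse events.
- **That enzyme rises during viremia before treatment are lost from the endpoint.** They precede DAA exposure, so they cannot be DAA-related events.
- **That the sections contradict each other.** All can be followed together. They are misaligned with the endpoint.

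**Conclusion.** The point holds in a limited form. No liver test is defined relative to DAA start, although the primary safety endpoint is about DAA treatment. If item 4.II runs from transplant, weekly cover of the therapy period falls from 96% for the earliest start to 30% for a day-3-positive patient treated at the eight-week limit, and to 0% for any start from day 84. Detection of laboratory liver events would then depend on start date, and a pooled incidence would mix unequal ascertainment.

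This rests on the inferred transplant anchor, the assumed 13-week quarterly spacing, and asymptomatic laboratory abnormalities being countable as adverse events. How many of the planned 55 patients would be affected cannot be computed from the documents. Early starters are well covered. It is worth correcting, but it does not undermine the study as a whole.

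**What to change.** 1. Name the anchor of item 4.II. If weeks of therapy were meant, one clause settles the matter.
2. Reconcile section III.c with items 2.III and 4 of section III.d, so that the liver measurements feeding the primary safety endpoint are defined relative to DAA start. Blood already drawn on therapy (the PCR samples and the routine CBC/Chem-7 draws) and at the post-treatment PCR can serve. Timing and frequency are for the sponsor and the centre to decide.
3. State whether laboratory abnormalities count as adverse events, and on what definition.
4. In section III.e, plan to report how many patients had a liver test in each therapy interval, and show adverse-event incidence alongside DAA start time.
5. If the schedule is left unchanged, state with the results that laboratory liver events on therapy were not systematically observed.

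The cost is a wording amendment, a few added assays on existing draws, and slightly more reporting. If the schedule is unchanged, only the wording and reporting remain.

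### The donor-group comparison is meant to confirm safety, but the visible analysis text offers only a p<0.05 threshold and plans no confidence interval for it or for the primary endpoints

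*Combined protocol and SAP*

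**What the plan says.** Section III.a gives the purpose of the 2018-2020 kidney chart review: "In order to confirm the safety of transplants using HCV+ kidneys, we will compare the outcomes" between viremic and non-viremic donors. It names three donor groups by antibody and PCR status but does not list the outcomes to be compared.

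The analysis text is in section III.e:

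- Item I: "Data presented will be mostly a descriptive data giving low number of enrolled patient and lack of adequate power analysis".
- Item III: "This will also be a descriptive analysis", followed by medians with interquartile ranges, percentages, and "Any p-values will be significant if <0.05". It opens with an empty bracket, so some text may be lost, and it may cover only the chart review.

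Section III.b sets a target of 55 prospective patients and adds: "Given the fact this is a proof of concept study, a sample size cannot be calculated based on power analysis".

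In section III.c the efficacy endpoint reads "Primary efficacy end point is the proportion of patients with undetectable HCV PCR at 12 weeks after completion of HCV treatment with Sofosbuvir/Velpatasvir". The primary safety endpoint is the incidence of DAA-related adverse events. Neither has an interval attached, and none appears elsewhere in the visible text.

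**The concern.** The purpose in III.a and the tools in III.e do not match. A significance threshold can flag a difference, but failing to reach it does not show that a difference is absent or small. With modest groups and infrequent events, a p-value above 0.05 is unsurprising even when outcomes are materially worse in one group. If that were the only inferential result reported beside the aim in III.a, it could be taken as reassurance that the data do not give.

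The same gap affects the primary endpoints. A bare percentage from 55 or fewer patients does not show how much uncertainty surrounds it. Section II.c hopes the results will persuade transplant leaders, procurement organizations and payers to make the strategy standard of care. Those readers need to see what the data can and cannot exclude.

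**Working it through.** **Nothing to reproduce.** The plan states no power, margin or interval, and gives 55 without a calculation. The check is therefore what the stated tools would show and what an interval would add.

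**Inputs from the documents:** threshold 0.05 (III.e item III); 55 prospective patients (III.b); endpoints (III.c).

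**Assumed inputs:** group sizes, event counts and outcome for the donor comparison. I use 12-month graft loss near 5%, borrowed from the secondary endpoint of graft survival in III.c. The viremic group is set at 30, 55 or 80 and the comparator at 100 or 300.

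**Donor-group comparison.** The p-value is two-sided Fisher. The interval is Newcombe's, built from the Wilson limits (l, u) of each proportion, with d = p1 - p2:

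- lower = d - √[(p1 - l1)² + (u2 - p2)²]
- upper = d + √[(u1 - p1)² + (p2 - l2)²]

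For 3/55 v 5/100:

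- p1 = 5.45%, Wilson 1.87% to 14.85%
- p2 = 5.00%, Wilson 2.15% to 11.18%
- d = +0.45 points
- lower = 0.45 - √(3.58² + 6.18²) = -6.7 points
- upper = 0.45 + √(9.40² + 2.85²) = +10.3 points
- Fisher p = 1.0

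Over the assumed range:

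| Viremic | Comparator | Difference (points) | 95% interval | Fisher p |
|---|---|---|---|---|
| 2/30 | 5/100 | +1.7 | -6.2 to +16.6 | 0.66 |
| 2/30 | 15/300 | +1.7 | -4.1 to +16.5 | 0.66 |
| 3/55 | 5/100 | +0.5 | -6.7 to +10.3 | 1.0 |
| 3/55 | 15/300 | +0.5 | -4.3 to +10.1 | 0.75 |
| 4/80 | 5/100 | 0.0 | -6.9 to +7.7 | 1.0 |
| 4/80 | 15/300 | 0.0 | -4.3 to +7.4 | 1.0 |

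No p-value falls below 0.66, yet an excess loss of 7.4 to 16.6 points stays within the interval.

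**Primary endpoints.** Exact (Clopper-Pearson) 95% limits for x of n are the 2.5% quantile of Beta(x, n - x + 1) and the 97.5% quantile of Beta(x + 1, n - x). With x = 0 the upper limit is 1 - 0.025^(1/n).

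- 0/55 adverse events: upper limit 1 - 0.025^(1/55) = 6.5%
- 53/55 cured: 87.5% to 99.6%

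The efficacy denominator may be below 55, because III.d item 2.III sends some patients to drugs other than sofosbuvir/velpatasvir. With an assumed 40, 38/40 cured gives 83.1% to 99.4%. If only 40 patients received any DAA, 0/40 adverse events has an upper limit of 8.8%.

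**The case against.** The strongest reply is that the plan does not claim inference. It calls the analysis descriptive, disclaims power, and mentions p-values only conditionally. Elsewhere the aim is to evaluate or explore, in a proof-of-concept study. Much of this stands. It makes the point a reporting gap and one over-strong verb, not a failed test. It does not remove the gap: a descriptive study can report intervals without any hypothesis or power, and they suit it better than a threshold.

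The empty bracket at the start of item III also counts. The claim is limited to the visible text, which contains no interval whether item III covers the chart review or the whole study.

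A reader might infer more than the documents support:

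- *That non-significance will be declared proof of safety.* The plan never says so; it is silent on how such a result would be read.
- *That the viremic group is restricted and the comparators are not.* Section III.b limits trial entrants, for example "Estimated post-transplant survival (EPTS) index >20% and <80"%, and limits donors by KDPI. But III.a draws all three donor groups from one chart review and does not confine the viremic group to trial enrollees. The imbalance is possible, not established.
- *That the comparison is unadjusted.* The plan does not say either way.
- *That a specific chance of missing a doubled risk can be attached to this study.* Any such figure would describe assumed sizes and rates, not the trial.
- *That missing post-treatment PCRs must count as failures.* That would redefine the primary endpoint and is a separate question; here it is at most a sensitivity analysis.

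**Conclusion.** The point holds as a mismatch between purpose and tools. The plan sets out to confirm safety, names only a significance threshold, and plans no interval in the visible text for the comparison or either primary endpoint. A non-significant result could not confirm safety.

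That conclusion does not depend on the illustrative counts; its size does. All figures for the donor comparison are assumptions. The primary-endpoint figures use the plan's own target of 55 as the denominator, with assumed event counts, and would be wider with fewer patients. This is a worthwhile, inexpensive improvement. It does not undermine the study as a descriptive proof of concept.

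**What to change.** 1. **III.e item I.** Report both primary endpoints with exact (Clopper-Pearson) 95% confidence intervals. State the number in each denominator, including how many patients who started sofosbuvir/velpatasvir had no PCR at 12 weeks after treatment.
2. **III.e item III.** Replace the p<0.05 sentence with group differences and 95% confidence intervals for viremic v non-viremic donors, and for viremic v each non-viremic subgroup if three groups are shown. Use survival-based estimates where follow-up is incomplete. Label any p-values exploratory, and state that no conclusion of safety will be drawn from a non-significant one.
3. **III.a.** Change the verb *confirm* to *describe*. Say whether the comparison is adjusted; if not, say that confounding by recipient and donor selection remains possible, since an interval does not remove it.

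**Cost.** Mostly wording and a little analysis work, with no larger sample. The reported certainty will look less favourable. If the data list in III.e item II also governs the 2018-2020 review, the compared outcomes must be added to it: it names no graft loss, death, eGFR or creatinine.
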